1 PROTOCOL SUMMARY

[figure not shown]
No text is to be entered in this section; rather it should be included under the relevant subheadings below. It may be useful to complete this section after the relevant sections in the protocol have been completed.

1.1 SYNOPSIS

Title:	Examining Flexibility in Attentional Control
Grant Number:	R15EY030247
Study Description:	Examination of healthy participant's behavioral responses to determine if cued attentional suppression and learned attentional suppression rely on the same mechanisms
Objectives :	The researchers will compare participants performance on a cued suppression task (distractor cue), learned suppression task (repeated distractor), working memory capacity, and inattentional traits.
Endpoints :	One day measurement of cued suppression task performance, learned suppression task performance, working memory capacity, and self-report inattentive traits.
Study Population:	Healthy adults, recruited from Lehigh University
Phase * or Stage:	Phase 0
Description of Sites/Facilities Enrolling Participants:	Lehigh University
Description of Study Intervention/Experimental Manipulation:	Correlational study of four measures: cued suppression, learned suppression, working memory capacity, and inattentive traits.
Study Duration :	4 months
Participant Duration:	60 minutes

1.2 SCHEMA

Flow Diagram

1.3 SCHEDULE OF ACTIVITIES

	Pre-screening (Pre-consent)	Visit 1 Day 1
Review Eligibility	X	
Informed Consent		X
Demographics		X
Outcome Evaluation		

2 INTRODUCTION

2.1 STUDY RATIONALE

Recent research has focused on two forms of distractor ignoring. In learned suppression, repeated salient distractors are presented and participants learn through experience to ignore the distractor color (Gaspelin & Luck, 2018). While salient distractors typically capture attention, learned suppression can lead to faster performance when a salient distractor is present compared to absent, suggesting that the salient distractor is suppressed. Other work on cued distractor suppression has demonstrated the existence of negative templates, also called templates for rejection (Arita, et al., 2012). Here, participants use their working memory to maintain cued colors, and then utilize top-down control to ignore items matching the distractor color. While both learned and cued suppression lead to ignoring of distractors, it is unclear if these two types of suppression rely on the same or different underlying mechanisms (Geng, et al, 2019).

2.2 BACKGROUND

Much of the research on visual attention has focused on how humans direct attention towards our goals (Desimone & Duncan, 1995). However, recent research has identified two ways in which attention can be configured to ignore distractors, also improving attentional performance. In learned suppression (Gaspelin & Luck, 2018), repeated salient distractors are presented, and over learning, these salient items can become ignored. Participants are not instructed to ignore the salient items, however they learn through selection history to ignore the salient items. In cued suppression (Carlisle, 2023), participants are explicitly told to ignore a cued color presented before the search array. Here as well, participants are able to direct attention away from the cued color. However, although both tasks rely on suppressing colored items, it is unclear whether they rely on the same mechanisms. Learned suppression is an implicit phenomenon, while cued suppression is based on explicit top-down control.

Here, the researchers will look for correlations between the amount of suppression generated in cued suppression and learned suppression. The researchers will also measure working memory capacity, as an index of overall cognitive control. And researchers will take a measure of everyday distraction, an inattentive traits scale. The researchers will examine the correlations between all of these measures to determine if cued and learned suppression have shared underlying mechanisms.

2.3 RISK/BENEFIT ASSESSMENT

No text is to be entered in this section; rather it should be included under the relevant subheadings below.

The following subsections should include a discussion of known risks and benefits, if any, to human participants. Text from the corresponding sections of the Human Subjects section of the grant application, and/or IRB package may be used here.

2.3.1 KNOWN POTENTIAL RISKS

The risks associated with the behavioral tasks are similar to working on a computer or playing a video game. They include possible eye strain, and boredom. Researchers will try to reduce the possibility of these risks by providing frequent breaks during the experiment (approximately every 5 minutes during data recording).

2.3.2 KNOWN POTENTIAL BENEFITS

There are no direct benefits expected for the participants, however many participants enjoy being able to learn more about how The researchers use behavioral responses to understand more about cognition.

2.3.3 ASSESSMENT OF POTENTIAL RISKS AND BENEFITS

Given that the risks are similar to daily tasks, the benefits to science are considered to outweigh the risks of the study.

3 OBJECTIVES AND ENDPOINTS

Provide a description of the study objectives and endpoints, as well as a justification for selecting the particular endpoints, in the table format included below. This will provide clear articulation of how the selected primary and secondary endpoint(s) are linked to achieving the primary and secondary objectives and an explanation of why endpoint(s) were chosen. Data points collected in the study should support an objective or have a regulatory purpose. Therefore, careful consideration should be given prospectively to the amount of data needed to support the study's objectives.

*An **objective** is the purpose for performing the study in terms of the scientific question to be answered. Express each objective as a statement of purpose (e.g., to assess, to determine, to compare, to evaluate) and include the general purpose (e.g., feasibility, acceptability, engagement of the intervention target, identifying mechanisms of action, mediation, moderation, efficacy, effectiveness, dissemination, implementation).*

*A study **endpoint** is a specific measurement or observation to assess the effect of the study intervention. Study endpoints should be prioritized and should correspond to the study objectives and hypotheses being tested. Give succinct and precise definitions of the study endpoints used to address the study's primary objective and secondary objectives (e.g., specific diagnostic tests that define safety or efficacy, clinical assessments of disease status, assessments of psychosocial characteristics, patient reported outcomes, behaviors or health outcomes). A full description of study endpoints, including administration, scoring, psychometrics, adjudication of endpoints, etc., belongs in **Section 8, Study Assessments and Procedures**.*

A putative mechanism of action is the theorized explanation for how the intervention functions.

Consider whether primary and secondary endpoints should be adjusted for multiple comparisons, family-wise error rates, alpha inflation, etc. Details of any such adjustments should be included in **Section 9.4.2, Analysis of the Primary Endpoint(s)** and **Section 9.4.3, Analysis of the Secondary Endpoint(s)**.

OBJECTIVES	ENDPOINTS	JUSTIFICATION FOR ENDPOINTS
Primary To assess the degree of relatedness between cued and learned suppression	Learned suppression performance, cued suppression performance, working memory capacity, inattentive traits	By measuring performance in both cued and learned suppression within the same individuals, the researchers can look for correlations indicating a shared underlying mechanism. Including measures associated with cognitive control (working memory capacity) and everyday distractability (inattentive traits), the researchers can further confirm whether shared mechanisms are at play.

4 STUDY DESIGN

4.1 OVERALL DESIGN

Hypothesis: Cued and learned suppression rely on separate underlying mechanisms. This is a Phase 0, single site study with a within-subjects design in healthy participants. Order of templates (intervention) within participants is counterbalanced.

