2 STATISTICAL CONSIDERATIONS

2.1 STATISTICAL HYPOTHESES

Researchers hypothesize that cued and learned suppression rely on separate underlying mechanisms, leading to no correlation in suppression between the two tasks.

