2.2 SAMPLE SIZE DETERMINATION

Data collection procedures

Researchers requested 75 participants in this study. 75 completed the task by the end of participant recruitment. Participants were at least 18 years old. It was a standard lab experiment. This study took 60 minutes to complete.

In this experiment, participants received verbal instructions from the experimenter before performing each task.

Both their color vision and their visual acuity have to be normal or corrected-to-normal (with glasses or contacts) (inclusion criteria).

No files selected

Sample size

A power analysis thus suggested that 48 participants would be sufficient (by using G*Power 3.1, when setting alpha error = to 0.05 and 90% power, with two-tailed testing). Researchers decided to include a larger sample size (75) to ensure enough power to detect the correlation, following participant exclusion.

Sample size rationale

Regarding the hypothesis on correlations, researchers anticipate discovering a moderate effect size of 0.45. This assumption is based on the previous studies discussed in the introduction, suggesting strong relationship between cued- and learned-suppression, as well as relationships with visual working memory and distractibility in everyday life thoughts.

A power analysis thus suggested that 48 participants would be sufficient (by using G*Power 3.1, when setting alpha error = to 0.05 and 90% power, with two-tailed testing).

Stopping rule

Researchers planned to use as many good participants as the researchers were able to collect within the sample of 75 requested. 21 participants were excluded for either bad accuracy in one of the cognitive tasks (n = 11) or for incomplete data recording (n = 10).

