2.4.2 ANALYSIS OF THE PRIMARY ENDPOINT(s)

Statistical models

To explore if the capacity to suppress cued distractors relies on the same mechanisms that the learned-suppression, Pearson correlation analysis will be performed between raw behavioral performance or indices (e.g., RT benefits and probe suppression) between the cued- and the learned-suppression task. In the same manner, to explore if the attentional suppression abilities (cued- and learned-suppression) were similarly associated with the visual working memory ability and the everyday life suppression ability, Pearson correlation has been used.

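### The cued-learned correlation ignores template order; if cue-block order differed between participants, this could modestly attenuate r, and the plan does not say what was counterbalanced

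*Combined protocol and SAP*

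**What the plan says.** Section 4.1 (Overall Design) says of the design: "Order of templates (intervention) within participants is counterbalanced". It does not say what the templates are, how many orders were used or how orders were assigned. Section 6.3, the place for measures against bias, is marked not applicable.

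Section 3 gives the primary objective as "To assess the degree of relatedness between cued and learned suppression". Section 2.4.2 (Analysis of the Primary Endpoint(s)) specifies "Pearson correlation analysis will be performed between raw behavioral performance or indices (e.g., RT benefits and probe suppression) between the cued- and the learned-suppression task". Neither there nor in section 2.4.1 is there an order term, a partial correlation or a sensitivity analysis for order.

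Both scores are contrasts within a person. The cued score compares the informative negative cue with the neutral cue; the learned score compares trials with and without the salient distractor (sections 6.1.1 and 2.4.1). The hypothesis in section 2.1 (Statistical Hypotheses) is separate mechanisms, "leading to no correlation in suppression between the two tasks".

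**The concern.** Section 4.2 justifies the within-subjects design by its protection of differences between conditions. That is an argument about means: averaged over participants, an order effect balances out. The primary quantity here is a correlation of individual scores, and in a correlation nothing is averaged out. If some participants did the negative-cue block before the neutral-cue block and others did the reverse, practice or fatigue would raise the cued benefit in one group and lower it in the other. The cued score would then carry variance that has nothing to do with suppression ability, and its correlation with any other measure would shrink.

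The direction matters because the study predicts no correlation. Attenuation leans towards that prediction, so a reader of a null result would want to know that order had been considered.

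**Working it through.** **The plan's own figure.** Section 2.2 (Sample Size Determination) says "researchers anticipate discovering a moderate effect size of 0.45" and sets the test "when setting alpha error = to 0.05 and 90% power, with two-tailed testing". By Fisher's z:

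N = ((1.960 + 1.282) / atanh(0.45))² + 3 = (3.2415 / 0.4847)² + 3 = 47.7, rounded up to 48.

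This reproduces the stated result: "A power analysis thus suggested that 48 participants would be sufficient".

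**Analysable sample.** The same section reports 75 participants and 21 exclusions, so n = 75 − 21 = 54. The figure 54 is derived, not stated.

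**Effect of order on r.** Assume two equally frequent orders, a cued score with SD 1 within each order group, and a difference of d between the group means. Each group sits d/2 from the overall mean, so order adds d²/4 to the variance of the cued score. If order does not touch the learned score, the covariance is unchanged and

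observed r = true r / √(1 + d²/4).

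Power is Φ(m − 1.96) + Φ(−m − 1.96), with m = atanh(r) × √(54 − 3). The second term is negligible here. The values of d are assumptions, because the documents report no order effect.

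| d (assumed) | √(1 + d²/4) | observed r | m | power |
|---|---|---|---|---|
| 0 | 1.000 | 0.450 | 3.461 | 93.3% |
| 0.2 | 1.005 | 0.448 | 3.441 | 93.1% |
| 0.5 | 1.031 | 0.437 | 3.342 | 91.7% |
| 0.8 | 1.077 | 0.418 | 3.178 | 88.8% |
| 1.0 | 1.118 | 0.402 | 3.047 | 86.1% |

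Using a t critical value instead moves the last entry to about 87%. A simulation of 20,000 replicates at n = 54 gave power of 92.0% and 89.4% for the unadjusted r at d = 0.5 and 0.8.

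**When the true correlation is zero.** The numerator is zero, so observed r is 0 for every d, and the false-positive rate stays at 5%. The simulation gave 5.0% and 4.7% at d = 0.5 and 0.8.

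**Effect of adjusting.** In the same simulations the partial correlation given order kept the false-positive rate at about 5% and power at about 93%. If order has no effect, replacing √51 by √(51 − k) for k order terms gives power of 93.3% for k = 0, 92.9% for k = 1 and 90.8% for k = 5.

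**The case against.** **Order may not differ between participants at all.** The sentence in section 4.1 says the counterbalancing is within participants. If each person received a balanced sequence, order adds little or no between-person variance. Section 6.1.1 says neutral cues come on other trials, which could mean that cues were intermixed and there was no block order. Against this, section 6.2.1 refers to task blocks, and the missing-data rule in section 2.4.1 provides for a participant who misses a whole cue condition. Blocked conditions are therefore plausible but not confirmed. This objection stands, and it makes the point conditional.

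**A reader might infer that order could create a false correlation.** That would need one order factor, such as task order, that varies between participants and shifts both scores. The documents describe none. They use the word template for cued control: section 2.1 (Study Rationale) ties negative templates to cued suppression, and a cited title in the references calls negative and positive templates two forms of cued attentional control. Learned suppression is never called a template. On that reading order acts on the cued score alone, which can dilute r but cannot produce it, so the documents do not support a claim of excess false positives.

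**A reader might also infer a larger dilution.** A shift of 0.75 SD either way takes 0.45 to 0.36 and power to 77%. But that is a gap of d = 1.5 between order groups, and nothing in the documents suggests an effect of that size.

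**The remedy could cost more than the problem.** This is true of a full six-order adjustment: 5 df costs 93.3 − 90.8 = 2.5 points, against a loss of 93.3 − 91.7 = 1.6 points from ignoring order at d = 0.5. It is not true of a single indicator, at 93.3 − 92.9 = 0.4 points.

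**The change comes late.** Section 2.2 (Sample Size Determination) already reports completed recruitment and exclusions, and section 2.4.1 reports factor-analysis results. An adjustment introduced now has to be labelled as an addition.

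**Conclusion.** The gap is real but modest, and it is conditional. The plan counterbalances an order, does not say which, and leaves it out of a between-person correlation. If cue-block order varied between participants, the unadjusted r may be attenuated: from 0.45 to about 0.44, 0.42 or 0.40 for assumed d of 0.5, 0.8 or 1.0, with power at n = 54 of about 92%, 89% or 86-87% against 93%. At d = 0.2 the effect is negligible.

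These figures assume two equal order groups, an effect on the cued score only, and a true r equal to the planning value. The unadjusted correlation is not shown to be invalid. The documents also do not say that each participant's order was recorded, so the adjustment depends on those records existing.

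**What to change.** - **Section 6.3:** replace the not-applicable entry with a statement of what was counterbalanced (cue conditions, tasks or both), whether cues were blocked or intermixed, which orders were used, and how they were assigned.
- **Section 2.4.2:** if cue-block order varied between participants, report the partial Pearson correlation of the cued and learned indices, adjusting for one indicator of whether the negative-cue block preceded the neutral-cue block, next to the unadjusted r. Do the same for the other correlations that use the cued index, namely those with working memory capacity and inattentive traits.
- **Labelling:** because data collection is already reported, call this an order-adjusted analysis added to the plan.
- **If each participant's sequence was balanced or cues were intermixed:** say so. No adjustment is then needed.

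**Cost.** Wording and 1 df. If order has no effect, power at r = 0.45 goes from about 93.3% to 92.9%. Avoid separate terms for all six orders of three cue conditions, which would cost 5 df and about 2.5 points. The single indicator captures most of what matters. Under an assumed linear drift across three blocks, the neutral-minus-negative position difference over the six orders is +1, +1, +2, −1, −1, −2, with variance 12/6 = 2. The indicator separates means of +4/3 and −4/3, with variance 16/9, which is 8/9 of the total.

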4.2 SCIENTIFIC RATIONALE FOR STUDY DESIGN

Within subjects designs are considered a desirable design in cognitive studies, if possible. Within-subjects designs ensure that differences between conditions are not driven by differences in the individuals assigned to each group.

4.3 JUSTIFICATION FOR INTERVENTION

Single-day designs are typical for the assessment of different attentional templates (Arita, et al, 2012; Carlisle & Nitka, 2019; Zhang & Carlisle, 2023).

4.4 END-OF-STUDY DEFINITION

A participant is considered to have completed the study if he or she has completed each of the tasks of the study.

5 STUDY POPULATION

5.1 INCLUSION CRITERIA

Healthy adults aged 18+ with normal or corrected-to-normal visual acuity, and normal color vision will be recruited. Participants may be recruited from the Lehigh University student body as well as the local area. Some participants will be recruited through the University's online participant recruitment system, SONA, where participants will see a brief description of the study and choose to sign-up. Researchers may also post notices on Lehigh's daily emails (these notices will contain the same text as the provided flier). Participants may also be recruited through fliers (see example flier) and word-of-mouth. Fliers may be posted on campus, or in the local community on public bulletin boards (e.g. in a grocery store). All fliers will explain what characteristics The researchers are looking for in our participants, and the compensation provided to our participants. These participants may email or phone the researchers to express their interest, and may be contacted by email or phone to schedule their participation, or be directed to sign up for the SONA experimental participation system. Individuals who choose to participate may let others know about the studies by word-of-mouth.

Researchers will not require that participants see the fliers themselves in order for them to participate, but will allow all participants who meet the requirements the opportunity to participate. If a participant would like to be contacted about further studies in our lab when they finish their experiment, The researchers may also add them to a lab database of potential participants. This lab database may receive emails to let them know about new studies The researchers conduct in the lab (emails will contain the same information included in the flier, as well as 'We are recruiting participants for a new behavioral study on attention').

5.2 EXCLUSION CRITERIA

An individual who meets any of the following criteria will be excluded from participation in this study:

1. Under age 18
2. Abnormal color vision
3. Visual acuity which is not normal, and has not been corrected to normal (20/20)

5.3 LIFESTYLE CONSIDERATIONS

- N/A

5.4 SCREEN FAILURES

Participants are pre-screened for eligibility before signing up for the study.

5.5 STRATEGIES FOR RECRUITMENT AND RETENTION

- *Participants will be recruited from the Lehigh participant pool, which includes students who are currently enrolled in PSYC 001 and fulfilling a research experience requirement for the class.*

6 STUDY INTERVENTION(S) OR EXPERIMENTAL MANIPULATION(S)

6.1 STUDY INTERVENTION(S) OR EXPERIMENTAL MANIPULATION(S) ADMINISTRATION

6.1.1 STUDY INTERVENTION OR EXPERIMENTAL MANIPULATION DESCRIPTION

Learned suppression : Participants will perform a learned suppression task, where the same color of salient distractor repeats across trials of a visual search task. Salient distractors do not appear on each trial, creating a baseline performance condition. Researchers will measure the effect of salient distractors by comparing reaction time on salient distractor present and salient distractor absent trials.

Cued suppression: Participants will perform a cued suppression task, where they receive an informative negative cue indicating the color of a large number of distractors on the upcoming search trials. On other trials they will receive a neutral cue which provides no information about the upcoming array. Participants will also perform a positive cue condition, where the cue indicates the color of the upcoming target. Researchers will examine the benefits from receiving the informative negative cue compared to the neutral cue.

Working memory capacity: Participants will perform a visual change localization task, leading to an estimate of their working memory capacity based on change localization performance.

Inattentive traits task: Adult Attention Deficit Hyperactivity Disorder (ADHD) Self Report Scale (used on healthy adults), Inattentive Traits subscale. Higher values indicate more ADHD-like inattentive trait symptoms (0-45).

